COVID-19 Enhancement Primary Aim: After co-design of the 3-session I-IMR module, we will evaluate the impact of the module by comparing participants assigned to I-IMR (n=75) to participants assigned to CDSMP (n=75) on the primary and secondary outcomes (**primary**: knowledge and use of measures to prevent contracting and spreading COVID-19; **secondary**: use of healthcare services for COVID-related concerns; perceived isolation and social disconnectedness).

Primary Hypothesis: I-IMR participants will demonstrate greater improvements in their scores on the primary outcome measure (a measure of knowledge and behaviors to prevent contracting and spreading COVID-19 developed for this project) compared to CDSMP participants.

Secondary Hypothesis: I-IMR compared to CDSMP participants will demonstrate less COVID-related health care service use and greater improvements in social connectedness.

Exploratory Aim: Explore differential response with respect to race/ethnicity (Black versus White adults); age (older versus younger adults); and psychiatric diagnosis (schizophrenia-spectrum vs. mood disorders).

Exploratory Hypothesis: Effect sizes for the I-IMR module versus generic support calls alone will be even greater among Blacks v. Whites, older (55+) v. younger adults, and people with schizophrenia-spectrum v. mood disorders.

3. Study Design

The proposed study is to compare I-IMR and CDSMP in improving outcomes of importance to the target population of people with SMI: optimizing personal physical and mental health, being an active agent in determining personal physical and mental health wellness goals, decreasing risk of early mortality, and minimizing use of the ER and hospitals. A secondary objective is to learn whether psychiatric diagnosis and/or age interacts with treatment, specifically, whether treatment effects vary more for participants with schizophrenia or older age. Consistent with a truly pragmatic trial, inclusion criteria are broad and exclusion criteria are limited. Participants will be randomized, stratified by diagnosis (schizophrenia spectrum vs. mood disorder) and age group (age 18-49 vs. age 50+).

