These interviews will inform development of the curriculum for the 3-session I-IMR module on COVID-19 and other viral diseases. This component of the project will also involve development of the primary outcome measure, given that no appropriate measure of COVID-19 knowledge and use of behaviors to avoid catching and spreading disease was available. After finalizing the curriculum for the 3-session I-IMR module, interventionists will be trained to deliver it by phone or video. We will record the sessions to permit supervision and fidelity assessment by the co-developers of I-IMR. All participants have already consented to audiotaping or videotaping of IIMR sessions. Research staff will conduct baseline, 6- and 12-week assessments by phone with all participants (75 I-IMR and 75 CDSMP participants). (Site Coordinators will first complete informed consent to participate in this project, by phone using the procedure described below). We will work with the statisticians from the I'M Well project to complete data analyses.

Site Coordinators will contact individuals who have been randomized to I-IMR and CDSMP to invite them to participate in this component of the project. I-IMR group participants will be offered the 3 session I-IMR module and asked to participate in a phone-based assessment no more than one week prior to receiving the intervention (baseline), a second assessment no more than two weeks after completing the 3 sessions (6 week assessment), and a third assessment approximately 12 weeks after receiving the last session of the module (12 week assessment). CDSMP group participants are receiving usual care, which includes generic supportive telephone calls from agency staff. They will be asked to participate in phone-based assessments on the same schedule as the I-IMR participants. For both groups (I-IMR & CDSMP), Site Coordinators will call participants to review a description of the project in the consent form. Consent to participate will be obtained by phone.

Interventions to be Compared

IIMR (Integrated Illness Management and Recovery vs. CDSMP (Stanford Chronic Disease Self-Management Program)

Overview of Integrated Illness Management and Recovery (I-IMR): I-IMR combines 4 evidence-based psychosocial interventions for SMI: (1) *psychoeducation*, which improves knowledge about

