Analysis for Aim 1: All analysis will be conducted on the full sample regardless of exposure to treatment (intent to treat). Our **primary hypothesis** in **Aim 1** is that I-IMR compared to CDSMP will be associated with greater improvements in physical health self-management abilities (Self-Rated Abilities for Health Practices) and physical health consumer activation (Patient Activation Measure). To test this hypothesis, we will fit generalized linear mixed-effects linear models (GLMM) with identity link functions and normal distribution specification. Treatment arm (I-IMR and vs. CDSMP), time (baseline, 4-, 8- and 12-month), and arm-by-time interactions will be specified as fixed effects. Intercept and time will be specified as random effects to take the correlated nature of the data resulting from repeated measures into account. The primary hypothesis of interest will be examined by testing if the arm-by-time interaction effect (difference in rate of improvement over 12 month) is significantly different from zero. Our **secondary hypothesis** is that I-IMR compared to CDSMP will have greater improvement in self-reported **physical health** functioning (PROMIS Global Health Measure). The same GLMM model will be used to test this hypothesis. Qualitative data for Aims 1 and 2 will be audio-recorded, de-identified and transcribed, and analyzed with ATLAS.ti using the “grounded theory” approach.⁸⁵ The Research Support Team will read data and develop operational definitions from transcript coding, a validated approach which allows for multiple perspectives.⁸⁵ Codes will be assigned to text, grouped, and checked for themes. The codebook will consist of *a priori* researcher-driven codes, derived from interviews and inductively derived codes from qualitative data.⁸⁵ Analyses will assess within group consensus or disagreement. Member checking will be employed to validate qualitative results and resolve any incongruent findings.

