Analysis for Aim 2: Our **primary hypothesis for Aim 2 is that** I-IMR compared to CDSMP will be associated with greater improvements in **mental health self-management abilities** (Illness Management and Recovery Scale⁸⁰); and **mental health consumer activation** (Patient-Activation Measure-MH⁸¹); and our **secondary hypothesis** is that I-IMR compared to CDSMP will be associated with greater improvements in self-reported **mental health** functioning (PROMIS Global Health Measure⁷⁹). We will use the same GLMM approach to test primary and secondary hypotheses for Aim 2.

Analysis for Aim 3: We hypothesized that (1) participation in I-IMR compared to CDSMP will result in greater reductions in emergency room (ER) visits and acute care hospital days compared to the 12 months before participation; and (2) greater reduction in 10-year cardiovascular mortality risk (ACC/AHA Cardiovascular Risk Score⁸²) over 12 months. To test **Aim 3** (1), we will compute the total number of ER visits and hospital days 12-months before intervention, and 12-months after intervention, and fit the same generalized linear mixed model (GLMM) but with log link function and Poisson, or negative binomial or zero-inflated distribution (depending on model fit) because the

outcomes are counts and are likely to be skewed with a cluster of zero values.⁸⁶ The arm, time (before vs. after) and arm*time interaction will be included as fixed effects, and the superiority hypothesis of I-IMR compared to CDSMP will be tested with the significance of the interaction term. For this analysis, because we cannot ensure covariates are balanced between two arms 12-months before randomization, we will test group (arm) balance with respect to demographic and clinical covariates. Depending on the number of imbalances we find, we will either include covariates in the model or use propensity score adjustment with inverse probability weighting to balance the groups.

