The same GLMM model will be used to test **Aim 3** (2), and the same fixed effects, intervention arm, time and arm*time interaction will be included in the model, but the time variable has four assessment points (baseline, 4-, 8- and 12-month), not two points. Thus, the outcome, 10-year cardiovascular mortality risk (ACC/AHA Cardiovascular Risk Score⁸²) is a proportion/percent, which is a continuous variable with limited range. The identity link function and normal distribution will be specified for this outcome. However, if outcome data does not include the lower and upper limits (0 and 1), the logit link function and beta distribution⁸⁷ will be specified because beta regression is more appropriate for percent and proportion outcomes within the 0-1 range.

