Analysis for Aim 4: In **Aim 4**, we compare I-IMR to CDSMP with respect to subgroup differences in self-management outcomes by ***mental illness subgroup*** (schizophrenia-spectrum vs. mood disorders) and by ***age*** (18-49 vs. 50+) based on our belief that greater cognitive limitations and comorbid health conditions may require more intensive and specialized self-management training consistent with I-IMR. We hypothesize that when comparing I-IMR and CDSMP, the difference in treatment effects will be greater for schizophrenia spectrum disorders compared to mood disorders; and greater for older (age 50+) compared to younger (age 18-49) participants with respect to: ***physical health self-management abilities and activation; mental health self-management abilities and activation*** and 10-year ***cardiovascular mortality risk reduction***. In this aim, we examine heterogeneity of treatment effects (HTE) using subgroup analyses. Because we pre-specified the 2 subgroups (diagnosis and age) and hypothesized the differential treatment effect between subgroups based on the literature, our approach is confirmatory (hypothesis driven) HTE analysis. To test HTE, we will use the same analytic models, GLMM for **Aim 1**, **Aim 2** and **Aim 3**, but we will include 3-way interaction terms (arm*time*group) in each model. A significant 3-way interaction effect will indicate the existence of the heterogeneity of treatment effects between subgroups. Following this step, we will conduct simple effect analysis to estimate treatment effect differences (a difference in slopes by time effect between arms) within each subgroup. Although our HTE analysis is hypothesis driven, we will report p-values for hypothesis testing for all subgroup analyses. We will also evaluate HTE by examining the magnitude of treatment effects with standard errors (clinically meaningful effect sizes) as outlined in PCORI Methodology Standards⁸⁸ and recommended by statisticians.⁸⁹

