| Carbon Monoxide Level | CO Analyzer PICO+ ¹¹⁵ | ✓ | | ✓ | ✓ | ✓ |
| Satisfaction Survey | | | ✓ | | | |

Table 2. COVID-Related Component Assessment Schedule

| Aim 1: | Instrument | Baseline | | 6 wk | 12 wk |
|---|---|----------|---|------|-------|
| Knowledge and use of measures to prevent catching and spreading virus | Measure to be developed as part of project | ✓ | | ✓ | ✓ |
| Aim 2: | | | | | |
| Use of healthcare for COVID-related issues | Self-reported service use and record review | ✓ | | ✓ | ✓ |
| Social determinants of health | UCLA Loneliness Scale ¹²⁴ | ✓ | | ✓ | ✓ |
| | Lubben Social Network Scale-6 ¹²⁵ | ✓ | | ✓ | ✓ |
| | Social Connectedness (items developed for this project) | ✓ | ✓ | ✓ | ✓ |

5. Study Progress Monitoring

Upon completion of trainings, promotion and recruitment will begin at both Seven Counties Kentucky and Centerstone Tennessee. [name] and [name], the site PIs in Kentucky, will facilitate the research team's access to the clinical treatment teams at Seven Counties Kentucky to identify potentially eligible participants and [name] will facilitate access at Centerstone Tennessee. In addition, the Site PIs will ensure that the research staff have access to information needed in the electronic medical record to efficiently screen potential participants. Both Site PIs will participate in the weekly project meetings with Dartmouth to discuss pre-implementation and implementation tasks as well as dissemination of outcomes for the project. [name], [name], and [name] will provide the administrative supervision to the site research staff and will periodically attend meetings of the Key Stakeholder Advisory Group and Consumer Advisory Group.

In addition to enrolling participants, the research staff hired for this project will be responsible for all data collection required for this project. The Research Coordinators and Research Interviewers will conduct baseline assessments with participants; while only the blinded Research Interviewer will conduct research assessments at 4, 8, and 12 months follow-up. The Research Coordinators will conduct the 8-week phone call to assess satisfaction with the study interventions. The Research Coordinators will manage an account to provide reimbursement to participants for completing research interviews. They will also assist in coordination of the Consumer Advisory Group meetings and the Key Stakeholder Advisory Group quarterly meetings.

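### The Gaussian models for Aims 1, 2, 3(2) and 4 give each randomised arm its own baseline mean: the planned test is valid, but a shared baseline mean would make it somewhat more precise

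*Combined protocol and SAP*

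**What the plan says.** The Combined protocol and SAP, Section 4, Analysis for Aim 1, sets out the model: "Treatment arm (I-IMR and vs. CDSMP), time (baseline, 4-, 8- and 12-month), and arm-by-time interactions will be specified as fixed effects". A participant-level intercept and a time effect are random. The hypothesis is examined by "testing if the arm-by-time interaction effect (difference in rate of improvement over 12 month) is significantly different from zero".

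The later aims inherit this structure:

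- **Aim 2:** "We will use the same GLMM approach to test primary and secondary hypotheses for Aim 2".
- **Aim 3(2), cardiovascular risk score:** "the same fixed effects, intervention arm, time and arm*time interaction will be included in the model", with four assessment points. The identity link and normal distribution come first; a beta model is the alternative.
- **Aim 4:** "we will include 3-way interaction terms (arm*time*group) in each model".

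None of these models has a baseline covariate or a constraint on the baseline means. The only covariate adjustment described is the imbalance-triggered one for the before-and-after counts in Aim 3(1).

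Section 3 (Study Design) says "Participants will be randomized, stratified by diagnosis (schizophrenia spectrum vs. mood disorder) and age group (age 18-49 vs. age 50" or over. These two factors also define the Aim 4 subgroups. On baseline assessment, Section 5 (Study Progress Monitoring) says "The Research Coordinators and Research Interviewers will conduct baseline assessments with participants". It does not say whether this happens before randomisation.

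**The concern.** An arm main effect alongside baseline as a response gives each arm its own fitted baseline mean. In a randomised comparison those means have the same expectation, provided baseline is measured before allocation can influence it. Because randomisation is stratified by the Aim 4 factors, this also holds within each subgroup level. The planned model spends information estimating a baseline difference whose true value is known to be zero, and chance imbalance at baseline feeds into the slope difference as noise.

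What is at stake is interval width for the four primary scales and for the Aim 4 three-way terms. For Aim 4 the plan itself notes that small subgroups raise the Type II error risk and says it will look at effect sizes and confidence intervals as well as p-values. Validity is not at stake.

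**Working it through.** **Inputs.** From the documents: visits at 0, 4, 8 and 12 months; 300 per arm; 20% attrition by month 12; random intercept and slope. The one piece of main-trial sample-size arithmetic reproduces: 600 × (1 − 0.20) = 480. No correlation, SD or effect size is given for Aims 1 to 4, so the covariances below are assumed. The baseline variance is set to 1 and the slope is per 12 months.

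**1. The planned contrast.** Reading the tested effect as a linear slope, with complete data, the estimate weights the arm differences at months 0, 4, 8 and 12 by c = (−0.9, −0.3, 0.3, 0.9). Under compound symmetry with correlation rho and n per arm:

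n × Var = 2(1 − rho) × (0.81 + 0.09 + 0.09 + 0.81) = 3.6(1 − rho).

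**2. Same contrast, shared baseline.** With categorical visits and d0 fixed at zero, the estimate is adjusted for the observed baseline difference. The variance removed (times n) is 2 × [0.9(1 − rho)]² = 1.62(1 − rho)². The proportional cut is 1.62(1 − rho)² / 3.6(1 − rho) = **0.45(1 − rho)**.

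| rho | variance cut | interval narrower by |
|---|---|---|
| 0.3 | 31.5% | 17% |
| 0.5 | 22.5% | 12% |
| 0.7 | 13.5% | 7% |
| 0.8 | 9.0% | 5% |

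The last column is 1 − √(1 − cut).

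**3. Random-slope covariance, as planned.** Let the error variance be 1 − intercept variance. The cut becomes

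(cov − 0.9 × error variance)² / (slope variance + 1.8 × error variance),

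where cov is the intercept-slope covariance. I took intercept variance 0.4, 0.5, 0.6 and 0.7, slope variance 0.1, 0.2, 0.3 and 0.4, and correlation −0.3, 0 and +0.2, which makes 48 sets.

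- Largest cut (0.4, 0.1, −0.3): (−0.06 − 0.54)² / (0.1 + 1.08) = 0.305.
- Smallest cut (0.7, 0.4, +0.2): (0.106 − 0.27)² / (0.4 + 0.54) = 0.029.
- Median: about 18%.

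Outside that grid the gain can disappear. With intercept variance 0.8, slope variance 0.1 and correlation +0.3, the cut is (0.085 − 0.18)² / 0.46 = 2%. With intercept variance 0.9 it is (0.09 − 0.09)² / 0.28 = 0. Over slope variances 0.1 to 0.4, these two intercept variances give 0% to 2%.

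**4. Dropout.** I repeated step 2 by generalised least squares with 80% complete and one fifteenth each last seen at months 8, 4 and 0 (missing at random assumed). The cuts relative to the planned model are about 27%, 19%, 11% and 7% at rho 0.3, 0.5, 0.7 and 0.8.

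**5. Aim 4.** For a subgroup share p, the variance of the three-way slope difference is multiplied by 1/p + 1/(1 − p) under either model. The proportional cut is therefore the same, if the covariance is the same in both subgroup levels.

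**6. Why not simply drop the arm term and keep time linear?** Under compound symmetry that version cuts the variance by 0.45(1 − rho)/(0.7 + 0.3·rho), or 26% at rho 0.5, slightly more than step 2. But it forces the arm difference onto a line through zero, and so changes what is estimated when the effect is not linear. At rho 0.5:

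| d4, d8, d12 | planned | shared baseline, linear time | step 2 contrast |
|---|---|---|---|
| 1, 1, 1 (held) | 0.90 | 1.06 | 0.90 |
| 1, 0.75, 0.5 (half fading) | 0.375 | 0.574 | 0.375 |
| 1, 0.5, 0 (fading to zero) | −0.15 | +0.09 | −0.15 |
| 0, 0, 1 (late) | 0.90 | 0.79 | 0.90 |

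**7. Validity of the planned test.** In 4,000 simulated trials (rho 0.6, slope SD 0.3, dropout missing at random, covariance known) the planned model rejected a true null 5.3% of the time, with Monte Carlo error about 0.35 points. It estimated a true 0.25 SD effect as 0.2506.

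**The case against.** The strongest reply is that nothing is broken. Arm, time and arm-by-time with baseline as a response is a standard model, its test is unbiased, and preferring a shared baseline is a refinement. That stands, and it is why the point is minor.

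The second reply is that the remedy can change the question. This is right for a shared baseline with linear time. A non-linear effect is plausible, because CDSMP runs six weeks, I-IMR has 16 sessions, and follow-up lasts 12 months. A reader might infer that deleting the arm term is almost free. Step 6 shows that it is not: the sign can change. The categorical version avoids this, since with complete data it keeps the planned weights for any shape of effect.

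The third reply is that the size of the gain is assumed. This also stands. The median of 18% describes the chosen grid, not this trial. The correlation of 0.05 in the COVID power paragraph belongs to a different outcome and schedule, and should not be borrowed.

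Finally, equality of baseline means depends on a fact that the documents leave unstated. Section 5 says who assesses baseline, not when. Nothing suggests that it follows allocation, but the constraint should wait for confirmation.

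**Conclusion.** The Gaussian models for Aims 1, 2, 3(2) and 4 leave some precision unused. Under compound symmetry and complete data, the same slope contrast could be estimated with 9% to 31.5% less variance for rho from 0.8 down to 0.3. Over the 48 random-slope sets the cut is about 3% to 31%. It is close to zero when intercept variance is 0.8 or more and intercepts and slopes correlate at +0.3. All of this assumes that baseline is completed before allocation is known.

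Two stronger readings are not supported. One is that the planned test is biased or invalid: its expectation under randomisation and the simulation both say otherwise. The other is that the trial would gain a stated amount of power: without a correlation or effect size for these aims, no figure can be attached to this trial.

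Valid here refers only to the handling of baseline; clustering by delivery group and multiplicity were not examined. Aim 3(1) is outside the point because it is a before-and-after count model. The COVID component is outside it because its baseline follows randomisation: "Site Coordinators will contact individuals who have been randomized to I-IMR and CDSMP to invite them to participate in this component of the project". The beta alternative for Aim 3(2) is also outside, because no calculation was made for it.

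**What to change.** 1. Confirm, and state in the SAP, that baseline is completed before allocation is known. If it is not, keep the planned model as primary.
2. If it is, fit visits as categories in the Gaussian models for Aims 1, 2 and 3(2), with one baseline mean shared by both arms, separate arm means at months 4, 8 and 12, and the planned random intercept and slope.
3. Test 0.9·d12 + 0.3·d8 − 0.3·d4, and say that this is the planned difference in rate. The text lists four time points but describes a rate, so naming the contrast also settles whether time is linear or categorical.
4. For Aim 4, drop arm and arm*group but keep group, so that each subgroup level has its own baseline mean shared across arms.
5. Use a shared baseline with linear time as a sensitivity analysis at most.
6. Leave Aim 3(1), the beta alternative and the COVID component as they are.

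The cost is SAP wording and a few more fixed effects: seven instead of four in the two-arm model (four visit means plus three arm differences, against intercept, time, arm and arm-by-time). No new participants, visits or data are needed. The change should be dated before anyone sees outcomes by arm; after that, it should be reported only as a sensitivity analysis.

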The proposed study will randomize people with serious mental illness to I-IMR (n=300) and CDSMP (n=300) to address the following four specific aims and hypotheses:

Aim 1: Compare the effectiveness of I-IMR to CDSMP with respect to our primary ***physical health self-management outcomes***.

Hypothesis 1: I-IMR compared to CDSMP will be associated with greater improvements in ***physical health self-management abilities*** (Self-Rated Abilities for Health Practices scale; SRAHP, and a qualitative interview) and ***physical health consumer activation*** (Patient Activation Measure; PAM); and (secondary hypothesis) greater improvement in self-reported ***physical health*** functioning (PROMIS Global Health measure).

Aim 2: Compare the effectiveness of I-IMR to CDSMP with respect to our primary ***mental health self-management outcomes***.

Hypothesis 2: I-IMR compared to CDSMP will be associated with greater improvements in ***mental health self-management abilities*** (Illness Management and Recovery Scale; IMRS, and a qualitative interview); and ***mental health consumer activation*** (PAM-MH); and (secondary hypothesis) greater improvement in self-reported ***mental health*** (PROMIS Global Health measure).

Aim 3: Compare the effectiveness of I-IMR to CDSMP with respect to ***emergency room and acute care hospital days***, and risk of ***10-year cardiovascular mortality***.

Hypothesis 3: Participation in I-IMR compared to CDSMP will be associated with fewer emergency room admissions and acute care hospital days over 12 months compared to the 12 months before participation; and greater reduction in 10-year cardiovascular risk score (ACC/AHA Cardiovascular Risk Score) from baseline to 12 months.

Aim 4: Compare I-IMR to CDSMP with respect to subgroup differences in self-management outcomes by **mental illness subgroup** (schizophrenia-spectrum vs. mood disorders) and by **age group** (18-49 vs. 50+).

Hypothesis 4: Comparing I-IMR and CDSMP, the difference in treatment effects will be greater for people with schizophrenia spectrum disorders compared to mood disorders; and greater for older (age 50+) compared to younger (18-49) participants with respect to: **physical health self-management abilities and activation** (SRAHP; PAM); **mental health self-management abilities and activation** (IMRS; PAM-MH); and 10-year ***cardiovascular risk reduction*** (ACC/AHA Cardiovascular Risk Score).

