Study participants will be 600 adults age 18+ with SMI (diagnosis of schizophrenia, schizoaffective disorder, bipolar disorder, chronic depression with moderate impairment in functioning, PTSD, and/or other serious anxiety disorders (e.g., Generalized Anxiety Disorder, OCD, Panic Disorder, Agoraphobia, etc.) receiving services at Centerstone (TN) and Seven Counties Services (KY) who reflect the racial, cultural, linguistic, and ethnic diversity of people with SMI in this agency. The race/ethnicity of consumers is as follows: White: 61%, Black: 30%, Hispanic: 3%, Other: 6%; 95% English speaking; and 52% Female. Eligibility for the study also includes: diagnosis of a chronic medical condition increasing risk of early mortality from cardiovascular or respiratory disease or diabetes, hyperlipidemia, hypertension, COPD [including emphysema], asthma, coronary artery disease, heart failure, tobacco dependence, obesity), chronic pain, and at least 1 ER visit or hospitalization within the past year (and/or 3 or more unscheduled outpatient visits) or judgment by the treatment team of substantial need for illness self-management training. Consumers who do not speak English will be excluded for logistical reasons. Consumers with either no, or a well-controlled medical condition will not be included. Individuals residing in a nursing home or other institution will be excluded given the focus on independent management of illness. Because I-IMR and CDSMP involve learning new skills, individuals with a chart diagnosis of dementia, or evidence of significant cognitive impairment as indicated by the Saint Louis University Mental Status Examination⁷³ score <20, will be excluded. Temporarily, during the COVID-19 pandemic, we will use the Telephone Interview for Cognitive Status (TICS)¹²⁰ because the SLUMS cannot be administered over the phone.

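### Aim 3 (1) tests ER visits and hospital days by a before/after interaction; adjusting the after-year for the before-year count is at least as precise at any before-after correlation

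*Combined protocol and SAP*

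**What the plan says.** Combined protocol and SAP, section 4, Analysis for Aim 3, part (1): "we will compute the total number of ER visits and hospital days 12-months before intervention, and 12-months after intervention". The counts are modelled "with log link function and Poisson, or negative binomial or zero-inflated distribution (depending on model fit". On the terms: "The arm, time (before vs. after) and arm*time interaction will be included as fixed effects". The superiority hypothesis "will be tested with the significance of the interaction term". Arm has its own free coefficient, so the fitted before-year means may differ between arms, and the before-year count is an outcome rather than a covariate.

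The same paragraph argues that balance in the year before randomisation cannot be guaranteed. It plans to test for balance and then says: "Depending on the number of imbalances we find, we will either include covariates in the model or use propensity score adjustment". The before-year count is not named as a pre-specified covariate.

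Hypothesis 3 (section 2) expects "fewer emergency room admissions and acute care hospital days over 12 months compared to the 12 months before participation". Eligibility (sections 3 and 9) includes "at least 1 ER visit or hospitalization within the past year (and/or 3 or more unscheduled outpatient visits) or judgment by the treatment team" that self-management training is substantially needed. Participants are randomised 1:1, stratified by diagnosis and age group. No before-after correlation, event rate, effect size or power is given for Aim 3.

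**The concern.** In a randomised trial the expected difference between arms in any year before randomisation is zero, so an observed difference is chance. The planned interaction subtracts that chance difference in full. A baseline-adjusted comparison subtracts only the part that predicts the after-year. If one year's use says little about the next, which is plausible for sparse and skewed hospital days, subtracting all of it adds more noise than it removes.

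Power is at stake for an outcome that section 3 lists among those important to participants. Interpretation is also at stake. Hypothesis 3 is framed as a fall from the prior year, and prior-year use is one route into the trial, so part of any fall within an arm would occur without benefit.

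**Working it through.** **Inputs.** 600 participants, 1:1, with 20% loss by 12 months (section 4, Evaluation of Attrition): 600 × 0.80 = 480, or 240 per arm. This reproduces the 480 in section 9, the only main-trial sample-size figure. A two-sided 5% level is stated only for the COVID component and is assumed here. The correlation r is not in the documents, so a range is used.

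**Step 1, general formula.** Let r be the correlation between a participant's before and after counts, and k the before-year coefficient of variation divided by the after-year one. On the log scale, in large samples, and taking the unadjusted after-year comparison as 1:
- variance of the interaction = 1 + k² − 2rk
- variance of the adjusted after-year comparison = 1 − r²
- difference = k² − 2rk + r² = (k − r)², which is never negative.

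**Step 2, equal variances (k = 1, a linear approximation).** The ratio is 2(1 − r)/(1 − r²) = 2/(1 + r).

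| r | interaction, 2(1−r) | adjusted, 1−r² | ratio |
|---|---|---|---|
| 0.1 | 1.80 | 0.99 | 1.82 |
| 0.3 | 1.40 | 0.91 | 1.54 |
| 0.5 | 1.00 | 0.75 | 1.33 |
| 0.7 | 0.60 | 0.51 | 1.18 |

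In power terms, the unadjusted after-year detects (1.960 + 0.842) × √(2/240) = 0.256 SD with 80% power. For that effect the interaction has 60%, 73% and 88% power at r = 0.2, 0.4 and 0.6. The adjusted comparison has 82%, 86% and 94%.

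**Step 3, against the unadjusted after-year.** 1 + k² − 2rk exceeds 1 only if r < k/2, which is 0.5 when k = 1. A simulation applied the entry rule under assumed parameters: lognormal frailty SD 0.8–1.6, latent year-to-year correlation 0.3–1.0, 0.5 admissions and 1.2 ER visits a year, mean stay about 8 days. It put k/2 at 0.36–0.44 for hospital days, so k is 0.72–0.88. At the midpoint k = 0.8 the Step 2 ratios become (1.64 − 1.6r)/(1 − r²): 1.48/0.99 = 1.49, 1.16/0.91 = 1.27 and 0.84/0.75 = 1.12 at r = 0.1, 0.3 and 0.5. The equal-variance figures therefore lie towards the upper end.

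**Step 4, dependence on persistence.** In that simulation the interaction's standard error, relative to the after-year alone, ran from 1.26 (r = 0.04) down to 0.68 (r = 0.75) for hospital days, and from 1.18 to 0.37 for ER visits. At the persistent end for hospital days the adjusted figure was 0.66, so the variance ratio was only (0.68/0.66)² = 1.06.

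**Step 5, size under weak persistence.** A second simulation used 480 participants and 400 replicates, and assumed that 75–100% of entrants had an ER visit or admission. SDs of the log rate ratio, interaction against adjusted:
- hospital days: 0.286 v 0.220, 0.298 v 0.242, 0.311 v 0.245; variance ratios 1.69, 1.52, 1.61
- ER visits: 0.128 v 0.123, 0.129 v 0.123, 0.146 v 0.149; variance ratios 1.08, 1.10, 0.96.

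Each SD carries a relative error of about 1/√800 = 3.5%, so 0.96 is not distinguishable from 1. For an assumed 35% reduction in hospital days, ln 0.65 = −0.431, and power is Φ(0.431/SD − 1.96): 28–33% for the interaction and 42–50% adjusted.

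**Step 6, falls without any effect.** In two settings of the first simulation, with no treatment effect and everyone entering on prior use, mean hospital days went from 8.93 to 7.64 (14% lower) and mean ER visits from 2.67 to 1.98 (26% lower). With 30% entering by another route the falls were 10% (6.53 to 5.87) and 18% (1.95 to 1.60).

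**The case against.** The planned interaction matches the wording of Hypothesis 3, and it is not biased. Regression to the mean from the entry rule affects both randomised arms alike, and no within-arm test is planned. That stands: this is a point about efficiency, not validity.

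A reader might infer that the entry criterion itself makes the test noisier than the after-year alone. The documents do not support this. They give no r, and the comparison reverses when use is persistent. On the planned log scale, the entry rule lowered the simulated ratio for hospital days in every setting (for example 1.38 to 1.26), because it reduced the before-year coefficient of variation more than the correlation. Low correlation drives the loss, not selection. Nor can it be said that before-year hospital days have few zeros. A participant can enter on an ER visit, unscheduled outpatient visits or team judgement with no hospital days, and the plan itself expects many zeros.

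In the second simulation the adjusted and unadjusted after-year SDs agreed to three decimals, so the covariate itself gained nothing there. The gain came from not subtracting the before-year. This fits r near zero: 1 + k² equals 1.52–1.69 when k is 0.72–0.83. The 1.5–1.7 range therefore belongs to weak persistence and is not a general forecast.

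Finally, a two-period model keeps the before-year data of people lost to follow-up, and an after-year outcome does not. This objection is fair, and the constrained version under the fix meets it.

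**Conclusion.** The plan gives up precision that the randomised design makes available. In the large-sample approximation the adjusted after-year comparison is at least as precise as the planned interaction at any r. With equal variances the interaction's variance is 1.82, 1.54 and 1.33 times as large at r = 0.1, 0.3 and 0.5, and less than that if k is below 1. A material gain is likely for hospital days if use is not persistent. For ER visits it was small in the simulation that compared the two analyses directly. All sizes rest on assumed correlations and event rates, and the formulas only approximate the planned count model. The planned test remains valid, but a fall within either arm should not be presented as benefit. The change is worth making before the data are analysed.

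**What to change.** In Aim 3 (1), make the after-year total the outcome of a log-link count model with arm, log(before-year count + 1), an indicator of any before-year event and the randomisation strata (diagnosis, age group). Test the arm effect. Alternatively, keep the two-period model but constrain the arms to a common before-year mean: time and arm-by-time terms, no arm main effect. This retains all randomised participants. In either version end the before-year at randomisation, since equality in expectation is guaranteed only up to that point.

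Let this pre-specified adjustment replace the choice between covariates and propensity weighting that depends on observed imbalance. Report before-year counts descriptively and state that within-arm falls are not evidence of effect.

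The cost is small. The before-year counts are already needed for the planned analysis, so only SAP wording changes. In the after-year version the test moves from arm-by-time to arm, and participants with incomplete follow-up need a log follow-up-time offset or the constrained version.
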